4.2 Scientific Rationale for Study Design

Given that participant variability (e.g., coagulation and platelet function) may impact study endpoints (e.g., device indwell time and haemolysis)²³, the current study utilizes a simultaneous paired experimental design to assess whether differences in device design (i.e., lengths of 1 inch and 1.75 inch) impact PIVC indwell time; unpaired analysis will be employed to investigate the effects of catheter gauge on PIVC indwell time. PIVC length was selected for paired analysis as it is hypothesized that longer PIVC catheters may extend indwell time based upon catheter tip location within the vessel, increased tip distance from insertion site, and reduced probability of accidental dislodgement. Although gauge is a factor that may impact indwell time, participant screening is conducted to only enroll those with catheter-to-vessel (C/V) ratios no greater than 45%; thus it is anticipated that gauge will have an effect less susceptible to participant variability and was selected for the unpaired analysis. As both device length and gauge are expected to influence haemolysis^{17,20} the study design enables evaluation of both design features.

Identification of device design factors that improve PIVC indwell time and decrease incidence of haemolysis during PIVC-based blood collection is of clinical significance due to the associated benefits for the patient (e.g., uninterrupted medical treatment, and decreased discomfort, pain and anxiety)^{28,29,33}, for the health care worker (e.g., reduced chance of needle stick injuries)²⁸, and for the healthcare institution (i.e., reduced cost of care)^{12,29}.

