10.6 Secondary Endpoint(s)

Linear mixed-effects models will be used to evaluate the following endpoints over time and determine the effect on PIVC indwell time for a given configuration (i.e., length/gauge):

- 1) cfHb concentration;
- 2) blood draw fill time;
- 3) blood flow velocities above or below the catheter
- 4) vessel dimensions; and
- 5) intravenous thrombus size.

Underlying normality assumptions will be verified and if not fulfilled non-parametric tests will be used. Multivariate analysis (to be defined in the SAP) will be employed to assess the effect of baseline characteristics on catheter indwell time and thus identify their power as predictive biomarkers using the following the independent variables including, but not limited to:

- 1) angle of insertion;
- 2) vessel dimension;
- 3) presence of side branches and/or intravenous valves;
- 4) age;
- 5) sex;
- 6) height;
- 7) weight;
- 8) BMI;
- 9) medical history questionnaire responses; and
- 10) exploratory endpoints.

A multiple-logistic regression analysis will be employed to assess the effect of baseline characteristics on catheter failure over a period of 72 hours and thus identify their power as predictive biomarkers using the independent variables including, but not limited to:

- 1) angle of insertion;
- 2) vessel dimension;
- 3) presence of side branches and/or intravenous valves;
- 4) age;
- 5) sex;
- 6) height;
- 7) weight;
- 8) BMI;
- 9) medical history questionnaire responses; and
- 10) exploratory endpoints.

A chi squared analysis will be employed to assess the proportion of individuals in each group (i.e., PIVC length and gauge) that have presence of the following at failure/end-of-protocol:

- 1) vein collapse;
- 2) intravenous thrombus; and

3) extravenuous thrombus.

All data will be evaluated using statistical modeling software (Prism, Release 8.3; GraphPad Software Inc., USA) or R (R 3.6.2 or higher). P-values ≤ 0.05 will be considered statistically significant.

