1.2.2 Secondary Objectives

- To assess haemolysis occurrence based on blood collection device, catheter device configuration.
- To evaluate blood draw fill time
- To determine the relationship, if any, between catheter blood draw patency indwell time and presence of intra/extravenous thrombi, catheter angle/tip location *in situ*, catheter length in vessel, vein depth from skin surface, C/V ratio, and vessel anatomy
- To evaluate changes in vessel dimensions, PIVC position (insertion angle and *in situ* tip position), and hemodynamics from baseline throughout indwell time

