2.6 Preliminary Analysis

In order to answer critically urgent business questions, a preliminary analysis will be performed by an independent statistician prior to the final database lock. This analysis will be limited to the analysis of the following specific endpoints:

- Indwell time (as described in section 5.2.1.1) and ranking of factor influencing indwell time (as described in section 5.2.2.3 by item 7)
- Haemolysis as a continuous measurement by device configuration and over time, including baseline venipuncture rate as relative comparator, as described in section 5.2.2.1 by item 1 (including the preliminary Boruta analysis)
- Rate of occurrence of Haemolysis by device configuration and over time, including baseline venipuncture rate as relative comparator, as described in section 5.2.2.1 by item 2 (including the preliminary Boruta analysis)
- Thrombus observation by device configuration over time, as described in section 5.2.2.3 by items 1, 2, 3, 4 and 7
- Incidence of failure modes for device removal, as described in section 5.2.1.2

The results of the preliminary analysis will be communicated by the independent statistician to [name] (Associate Director - Biomedical Engineering) who will be responsible for sharing them with [name] (Director - Product Development Engineering), select MDS designees, and [name] (Director/Principal Scientist - Parenteral Research). Preliminary analysis will not be shared beyond those required for making time-critical business decisions on behalf of the MDS business unit.

Every GCD employee involved in the study execution, especially the lead study statistician, as well as all site employees involved in the study execution, will remain blinded to the results of this preliminary analysis until database lock.

It is understood by all parties that the results of this primary analysis will be subject to confirmation after database lock and fulfillment of all the processes related to data quality described in the Data Management Plan.

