3. Rate of occurrence measured using the results of the AU480 Analysis at each time point listed in red in Table 2.7.1. Samples will be considered positive for haemolysis for AU480 output of + (50-99mg/dL), ++ (100-199mg/dL), +++ (200-299mg/dL), ++++ (300-500mg/dL) and +++++ (>500mg/dL), i.e. anything different from N (<50mg/dL)². A logistic mixed effect model will be used with haemolysis occurrence as response and subject as random effect. Time, gauge, length, vacutainer volume and baseline (at D1.2) cfHb will be fixed effects. Examples of the table summarizing occurrence rates per device per time point and associated graphical representation are provided in Appendix A by Table A.10.2 and in Appendix B by Figures B.4.1 and B.4.2, respectively. Contrast based multiple comparisons will be used to compare haemolysis rate between conditions (between gauge, between length) at each timepoint.
4. Rate of occurrence measured using the results of the visual assessment at each time point listed in red in Table 2.7.1. Samples will be considered positive for haemolysis for visual values $\geq 50\text{mg/dL}$, as shown on the reference chart. A logistic mixed effect model will be used with visually observed haemolysis occurrence as response and subject as random effect. Time, gauge, length, Vacutainer tube volume and baseline (at D1.2) cfHb will be fixed effects. An example of the table summarizing occurrence rates per device per time point is provided in Appendix A by Table A.10.2. Graphical representation will be similar to the ones given as example for the AU480 analysis. Contrast based multiple comparisons will be used to compare haemolysis rate between conditions (between gauge, between length) at each timepoint.

In each case, i.e. for cfHb, AU480 and visual assessment, modeling will be preceded by an assessment of the importance of potential covariates using the Boruta algorithm. The covariates of interest will include,

¹A separate assessment of the relationship between the cfHb and AU480 measurements will be performed in order to check the validity of this threshold, which could be modified upon review of these results.

²A separate assessment of the relationship between the cfHb and AU480 measurements will be performed in order to check the validity of this threshold, which could be modified upon review of these results.

but will not be limited to:

- Presence of thrombus
- Size of thrombus
- Proximity of thrombus to tip of catheter
- Draw rate

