5.2.2.2 Blood draw fill time

It is hypothesized that:

- The blood draw duration observed for blood samples (all vacutainers, at all timepoints) collected from shorter catheters will be decreased when compared to longer catheters of the same gauge.
- The blood draw duration observed for blood samples (all vacutainers, at all timepoints) collected from smaller gauge (larger bore) catheters will be decreased when compared to larger gauge (smaller bore) catheters of the same length, over time.
- The blood draw duration observed for blood samples (all catheters, at all timepoints) collected into greater volume vacutainers will be increased when compared to smaller volume vacutainers.

A linear mixed effect model will be used with blood draw fill time as response and subject as random effect. Time, device configuration (gauge, length and their interaction), Vacutainer tube volume and baseline (at D1.2) blood draw fill time will be fixed effects. Contrast based multiple comparisons will be used to compare blood draw fill time between conditions (between gauge, between length) at each timepoint. Example tables for summary statistics (overall and per time point for each Vacutainer tube volume are given in the Appendix section by Table A.9.1 and Table A.9.2, respectively. Graphical representations of distribution of blood draw time per device is provided in Figure B.5.1 and of average blood draw time is shown in the Appendix section by Figure B.5.3. Example tables for ANOVA tables (Table A.9.3) and multiple comparisons (Table A.9.4) can be found in the Appendix A

5.2.2.3 Relationship between catheter blood draw patency indwell time and presence of intra/extravenous thrombi, thrombus length, thrombus type catheter angle/tip location *in situ*, catheter length in vessel, vein depth from skin surface, C/V ratio, and vessel anatomy

Relationship, if any, will be assessed through the computation of:

1. Summary statistics stratified by indwell time considered as a discrete variable (0, 6, 24, 30, 48, 54, 72 hours)
2. Scatter plot showing time between initial Thrombus observation to time of removal per Device Configuration
3. Bar plot showing percentage of thrombus for each time point per device configuration
4. Scatter plot showing thrombus length as a function of time grouped by device configuration
5. Relationship between flush technique and presence of Thrombus

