6. Summary statistics and boxplot showing time between time of initial thrombus observation and device removal per device configuration

7. Importance of covariates will be computed with Boruta algorithm with a survival random forest model (an example output from the algorithm is provided in the Appendix by Figure B.7.1).
8. Test of predictive performance for the most important features (confirmed by the Boruta algorithm) using a leave-one-out strategy

In addition to the variables used in the primary endpoint survival model (device gauge and length), investigated baseline characteristics will be:

- Venous thrombosis
- Thrombus Length
- Thrombus Type
- Angles of insertion (Acute Inferior and Superior)
- Catheter to vein (C/V) ratio
- Catheter length in vessel
- Presence of side branches and/or intravenous valves
- Age
- Gender
- Height
- Weight
- BMI
- Dominant arm
- Medical history questionnaire responses
- Exploratory endpoints:
 - Vein collapse
 - Phlebitis
 - Dislodgement
 - Extravasation
- item Screening Blood Testing (as provided by Blood Testing CRF)
 - Coagulation Panel: PT & aPTT
 - Platelet Aggregometry: ADP, TRAP & Collagen Induced Maximal Amplitude
 - Blood Screening: Blood Glucose & Triglycerides
 - Liver Panel: ALT Average Measurement & AST Average Measurement

The Boruta algorithm does not require specific formatting and generally works well with continuous and categorical variables. In some cases, it might be interesting to move from continuous format to a categorical one (e.g. age) depending on the final analysis. Categorization rules will be detailed whenever performed.

5.2.2.4 Evaluation of changes in vessel dimensions, PIVC position (insertion angle and *in situ* tip position), and haemodynamics from baseline throughout indwell time

These will be evaluated using:

- C/V ratio
- Catheter Length in Vessel (mm)
- Catheter Insertion Angle - acute inferior border angle (deg)
- Catheter Insertion Angle - acute superior border angle (deg)
- Blood Draw Time (sec)
- Blood Flow Velocity (cm/sec)
- *In situ* tip position (Mid-Stream & Wall Contact)

For each of these characteristics, summary statistics by indwell time considered as a discrete variable (0, 6, 24, 30, 48, 54, 72 hours) and line and bar plots will be generated on average for continuous and by proportion for categorical responses, respectively.

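### The SAP's factor list for ranking predictors of indwell time leaves out tip position and vein depth, both named in the objective it serves

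*SAP*

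**What the plan says.** One secondary objective (SAP 1.2.2, Protocol 3.1) is to relate indwell time to intravenous and extravenous thrombi and to "catheter angle/tip location *in situ*, catheter length in vessel, vein depth from skin surface, C/V ratio, and vessel anatomy". The heading of SAP 5.2.2.3 repeats these factors.

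SAP 5.2.2.3 then lists eight outputs. Item 7 reads "Importance of covariates will be computed with Boruta algorithm with a survival random forest model", and item 8 tests the predictive performance of the features that item 7 confirms. The factors are introduced by "In addition to the variables used in the primary endpoint survival model (device gauge and length), investigated baseline characteristics will be". The list names:

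- venous thrombosis, thrombus length and thrombus type;
- insertion angles, C/V ratio, catheter length in vessel, side branches and valves;
- demographics, dominant arm and medical history;
- four complications;
- screening bloods.

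It contains neither tip position nor vein depth.

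Protocol 4.2 gives as a reason for studying length that "longer PIVC catheters may extend indwell time based upon catheter tip location within the vessel", and adds two more: a tip further from the insertion site and a lower chance of accidental dislodgement. Protocol 4.1 allows the study to be stopped after five participants if tip positions are not distinct between lengths. SAP 2.6 includes in the analysis before database lock the "ranking of factor influencing indwell time (as described in section 5.2.2.3 by item 7" of that section.

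**The concern.** The analysis written for this objective does not include two of the factors that the objective names. Tip position is the more important of the two. It is one of three stated reasons why length might matter, it is the subject of the early check that can stop the study, and it is already collected.

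If the plan is followed as written, the ranking cannot say whether tip position predicts indwell time. Correlated variables, such as insertion angle, catheter length in vessel or nominal length, may be ranked in its place. The same ranking goes to decision-makers before database lock, and adding tip position after that release would be post hoc.

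**Working it through.** No figure in the plan bears on this point (the log-rank power in SAP 2.4 plays no part), so the check sets the texts side by side.

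**1. Objective against list.**

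| Element of the objective (SAP 1.2.2) | On the SAP 5.2.2.3 list? |
|---|---|
| Intravenous thrombus | Yes (presence, length, type) |
| Extravenous thrombus | No |
| Catheter angle | Yes (inferior and superior) |
| Tip location in situ | No |
| Catheter length in vessel | Yes |
| Vein depth | No |
| C/V ratio | Yes |
| Vessel anatomy | Yes (side branches, valves) |

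Eight elements less three gives five covered.

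**2. Is the list closed?** The haemolysis list in SAP 5.2.2.1 opens "The covariates of interest will include" and goes on to say that it is not exhaustive. Protocol 10.6 introduces its own list for indwell time with "following the independent variables including, but not limited to". The 5.2.2.3 list has no such wording. The Protocol 10.6 list, though open, does not name tip position or vein depth either.

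**3. Does another section enter either factor as a predictor of indwell time?**

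- SAP 5.2.1.1 (Cox model): device, with gender, age, BMI and dominant arm as covariates. No.
- SAP 5.2.2.4: tip position is summarised by time and is the response in a logistic mixed model. Not a predictor.
- SAP 5.2.3.1 (Boruta): removal reasons, handling descriptors and complications. No.
- SAP 5.2.3.2 (Boruta): peak flush pressure and flush duration. No.
- SAP 5.2.4: a general rule to start with all factors, which names neither. No.

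The plan therefore tests whether length changes tip position (5.2.2.4) and whether length changes indwell time (5.2.1.1). It does not test whether tip position is related to indwell time.

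**4. Is tip position available?** Yes. Table 2.7.1 schedules it at every ultrasound time point. SAP 5.2.2.4 defines it as mid-stream and wall contact, and both appear in mock Table A.3.1 and Listing C.0.4. D1.1 precedes insertion, so D1.3 is the first usable scan. Calling the listed factors baseline characteristics does not explain the omission, because insertion angle and catheter length in vessel also exist only once the catheter is in place.

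**5. Is vein depth available?** Unclear. The protocol synopsis names it as an endpoint. Protocol 7.4 gives no method for it, and in the SAP it appears only in the objective, its restatement in 2.8.2 and the 5.2.2.3 heading.

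**The case against.** The best reply is that this is a gap in wording within one exploratory feature list of a feasibility study that has no acceptance criteria. The protocol's list is open, SAP 5.2.4 speaks of including all factors, and item 1 of 5.2.2.3 gives summaries by indwell time under a heading that names both variables. Angles and catheter length in vessel are partial proxies for tip position, and dislodgement, another stated mechanism, is on the list. The example plot for item 7 (Figure B.7.1) is not shown, so its features cannot be checked.

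Much of this limits the point without removing it. The general rule and the open protocol list name neither factor, descriptive summaries do not rank or test anything, and a proxy is no reason to leave out the variable itself when it is collected.

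Four stronger readings are tempting, and the documents do not support them:

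- **The ranking fails the whole objective.** It still serves the five elements that are listed.
- **Tip location is the trial's mechanism.** Protocol 2.1 and 4.2 give it as the first of three.
- **Vein depth goes unmeasured.** Protocol 7.4 also lacks a method for mid-stream and wall contact, yet both are tabulated. Table 2.7.1 does not itemise angle or catheter length either. The case report forms are not among the documents.
- **Adding tip position would show whether wall contact causes failure.** Boruta importance, as the note to Figure B.7.1 says, is predictive.

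**Conclusion.** The point holds in a limited form. Three of the eight elements of the objective are missing from the list. For tip position, the ranking in item 7, the check in item 8 and the early release under SAP 2.6 cannot assess the relation that the objective asks about. For vein depth, neither an analysis nor a measurement method is given. Extravenous thrombus is a different case: it is observed only once the catheter is out, so it cannot serve as a baseline predictor.

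A reader might count only the geometry factors in the heading and report two of six. That is a chosen subset and it overlooks extravenous thrombus.

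The conclusion assumes that the 5.2.2.3 list is meant to be complete, as its wording indicates, and that its thrombus entries mean intravenous thrombus, the only kind defined as an ultrasound finding in SAP 5.1.4. The primary log-rank and Cox analyses are unaffected. The change is worth making because it costs almost nothing and should precede the preliminary analysis.

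**What to change.** - **Tip position.** Add mid-stream (yes/no) and wall contact (yes/no), one value per catheter from D1.3, to the 5.2.2.3 list, and apply the same list to the ranking in SAP 2.6. State that importance is read as predictive. Change in tip position over time stays in 5.2.2.4. Cost: a SAP edit, with no new data.
- **Vein depth.** Confirm whether it is recorded, or whether it can be read from the stored longitudinal B-mode images (this needs the skin surface in view, which the documents do not confirm). If so, add it to the list and put a method and time point in Protocol 7.4. If not, remove it from the objective and give the reason. Cost: at most one extra reading per catheter on existing images, or a text change.
- **Extravenous thrombus.** Report its association with indwell time separately, as a finding at removal. Cost: one sentence in the SAP.

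All three should be settled before the preliminary analysis is run.

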5.2.3 Statistical Analysis of Exploratory Endpoints

5.2.3.1 Incidence of complications prompting device removal

Assessment of the incidence of reasons for removal, device handling descriptors and complication prompting device removal will include assessment of the frequency of occurrence of the following events:

- Reasons for removal:
 - End of study
 - Accidental Dislodgement
 - Flush Failure
 - Blood Draw Failure
 - Adverse Event
- Device handling descriptors:
 - Failure modes for Flush/Draw (2/6mL) by Device configuration
 - Success of specific remediation steps
 - Remediation occurrence rate by day and percentage of success
- Vein collapse
- Phlebitis
- Presence of Venous thrombosis
- Catheter Dislodgement from Vein
- Extravasation
- Accidental removal
- Catheter Dislodgement from Vein

For each of these characteristics, summary statistics by indwell time considered as a discrete variable (0, 6, 24, 30, 48, 54, 72 hours) and longitudinal line and bar plots will be generated on average for continuous and by proportion for categorical responses, respectively.

Lineplots will be similar to the example provided for cfHb in Figure B.3.2 and bar plots will be similar to the example provided for Haemolysis occurrence in Figure B.4.1, both represented in Appendix B.

Relationship between the occurrence of these events will be investigated using complementary approaches:

- Predictive Power over time (similar to Kramer's V but no need to transform variables)
- Boruta algorithm with a survival random forest model (an example output from the algorithm is provided in the Appendix by Figure B.7.1) where the variables coding for these events will be predictors.
- Boruta algorithm applied at each time point with failure up to current time point as response. A graphical representation of feature importance vs time will be generated similar to the one provided in the Appendix by Figure B.7.2
- Kramer's V evaluated at each time point and represented as a function of time (which will require categorization of continuous variables, to be performed *ad hoc*). A graphical representation of pairwise feature association Kramer's V vs time, similar to the one provided for the Boruta algorithm output represented in the Appendix by Figure B.7.2 will be provided.

Based on the outcome of these exploratory steps, models might be used to investigate further the relationship between these variables and indwell time.

